6. STATISTICAL ANALYSES

The total number of patients in the following data sets overall and among the study country will be tabulated:

- All screened set and screening failures.
- All enrolled set and patients that withdrew from the study at visit 1.
- Full analysis set.
- Patients that withdraw from the study at each stable visit and patients that completed the study.

In addition, screening failures will be summarized according to the reason for failure.

Withdrawal status will be summarised according to the reason for withdrawal. The number of withdrawn patients will be tabulated by study visit and overall.

6.1. Analysis of demographics/baseline characteristics

The analysis of demographic/baseline characteristics will be performed on the FAS and on the all enrolled set only if the percentage of enrolled patients excluded from the FAS is 5% or more.

The following characteristics at enrolment will be summarized using descriptive statistics:

- Demographics such as age at enrolment, sex and race.
- Present and past medical history.
- History of AECOPD within the previous year (overall and by AECOPD severity).
- Pre- and post-bronchodilator spirometry results.
- COPD status using the GOLD grade.
- Smoking/biomass exposure history status.
- Selected results and several risk factors from the ATS-DLD-78-A questionnaire.
- Physical examination/vital signs results such as height, weight, BMI, heart rate, respiratory rate, systolic and diastolic blood pressure.
- Chest X-rays results.
- Intercurrent comorbidities (reported at visit 1)
- History of pneumococcal and influenza vaccination (reported at visit 1)

CONFIDENTIAL

201112 (EPI-NTHI-001 BOD APA)
 Statistical Analysis Plan Amendment 2 Final

The following descriptive statistics will be adopted:

- The frequency and the percentage of each category will be reported for categorical variable.
- Number of non-missing observations, mean, median, standard deviation, minimum and maximum will be provided for quantitative variable.

All tables will be also generated by country.

Demographics and baseline characteristics will be also summarized for study sample for interim analysis.

6.2. Analysis of primary objective

The analysis of the primary objective will be performed on the FAS.

Average proportion of patients with sputum samples positive for bacterial or viral pathogens overall and for specific species, and its exact 95% confidence interval (CIs) will be computed at any stable scheduled visit and at any exacerbation visit for the entire study period. In addition, the average proportion of sputum samples positive for bacterial and viral pathogens overall and for specific species, and its 95% confidence interval will also be computed at any stable scheduled visit and at any exacerbation visit for the entire study period. Confidence intervals will be estimated using a Generalized Estimating Equations (GEE) model assuming a binomial distribution for the response variable with logit as link function and a compound symmetry correlation matrix (exchangeable structure) to account for the within-patient correlations (Liang, 1986) (more details in section 6.2.1). If the GEE model will not run due to only one level of the outcome variable, the exact 95% confidence interval will be computed. Proportion of patients with sputum samples positive for bacterial/viral pathogens overall and for specific species, will be computed, with exact 95% CIs, at each stable* scheduled visit (visit 1, visit 2, visit3) and at each exacerbation visit confirming acute exacerbation**.***.

* A confirmed stable visit will be defined as a scheduled study visit for which the investigator confirms in the eCRF that the patient is stable/has recovered from a previous exacerbation.

** If an AECOPD occurs at the time when one of the scheduled [stable] study visits is planned, it should be handled and recorded as an AECOPD visit. If possible, the stable study visit should be re-scheduled to a later date, within the ± 14 days' time window from the scheduled appointment, when the patient is stable again.

*** The definition of acute exacerbation of COPD (AECOPD) event is detailed in section 12.

CONFIDENTIAL

201112 (EPI-NTHI-001 BOD APA)
 Statistical Analysis Plan Amendment 2 Final

In details the following pathogens will be evaluated:

- Bacteria including, but not necessarily limited to, *H. influenzae**, *M. catarrhalis*, *S. pneumoniae*, *S. aureus*, *P. aeruginosa*, *K. pneumoniae* and *A. baumannii* by bacteriological methods (culture).
**H. influenzae* positive cultures will be further characterized to differentiate *H. haemolyticus*, typeable *H. influenzae* and non typeable *H. influenzae* by PCR assay.
- Viruses including, but not necessarily limited to, RSV, parainfluenza virus, enterovirus/ HRV, metapneumovirus, influenza virus, adenovirus, bocavirus and coronavirus using qualitative PCR.

Patients providing a sputum sample as per protocol are all evaluable patients (*i.e.* those meeting all eligibility criteria and complying with procedures described in the protocol*, **). According to protocol, the interval of ± 14 days for any scheduled visit will not be a criterion for exclusion from the analyses. The number and percentage of patients with a stable visit within and without this time window will be presented.

* *Patients attending a study visit and providing sputum sample.*

** *Patients using antibiotics on a continual basis (defined as more than 1 month in total) will be allowed to continue study participation, but may be eliminated from the analyses.*

If more than 10% of sputum samples have bad quality (as defined in section 11.2.3), the analyses for primary objective will be repeated in the subset of sputum samples of good and moderate quality.

An interim analysis will be performed when at least 40 AECOPD sputum samples are collected. This interim analysis will compute the rate of sputum sample positive any bacterium and by species (including Hi, NTHi and Mcat).

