^j Only if clinically indicated to exclude another cause of worsening of symptoms (e.g. pneumonia). If a chest X-ray is clinically indicated but a chest X-ray/ CT scan has already been taken for that AECOPD as part of medical care before the study AECOPD visit takes places, the results of that chest X-ray/ CT scan can be used. All cases of pneumonia (including all signs and symptoms assessed to confirm pneumonia) should be documented in the eCRF.

^k Sputum can be collected spontaneously or can be induced, as per investigator judgement. Sputum sampling should only be done if, in the opinion of the investigator, it is safe for the subject.

^l Physical examination should be done only if necessary by the investigator or delegate.

^m AECOPD severity grading as indicated in Table 2.

ⁿ Non-serious AEs will be recorded in the eCRF and will not be entered into the safety database.

^{*} Refer to Table 10 for description of which AE/SAEs are collected in this study.

Table 6 presents the intervals between study visits.

Table 6 Intervals between study visits

Interval	Optimal length of interval	Allowed interval ¹
Screening Visit (pre-Month 0) → Visit 1	± 14 days	≤42 days before Visit 1
	Scheduled study visits	
Visit 1 (Month 0) → Visit 2 (Month 6)	182 days	175 - 203 days
Visit 2 (Month 6) → Visit 3 (Month 12)	182 days	175 - 203 days
AECOPD-driven study visit(s) and/ or phone contacts		
Onset AECOPD symptoms → AECOPD Visit	-	max 96 hours ²

¹ If an AECOPD occurs at the time one of the scheduled study visits is planned, the stable study visit should be rescheduled to a later date, when the subject is stable again and within the time window specified. In consultation with GSK, the concluding visit (Visit 3, Month 12) may however exceptionally be conducted outside of the allowed interval if necessary by the investigator.

² AECOPD visits will be scheduled as soon as possible after the onset of AECOPD symptoms as recorded in the electronic Diary Card or confirmed by the subject (maximum 96 hours after and, if applicable, preferably before starting treatment with antibiotics).

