7. ANALYSIS INTERPRETATION

All analyses are descriptive. The use of these descriptive analyses will be limited to supportive analysis or hypothesis generation.

CONFIDENTIAL201112 (EPI-NTHI-001 BOD APA)
Statistical Analysis Plan Amendment 2 Final**8. CONDUCT OF ANALYSES****8.1. Sequence of analyses**

The analyses will be performed in two steps:

- An interim analysis will be performed when at least 40 AECOPD evaluable sputum samples are available. It will include all data available at the time of analysis. The rate of positive samples will be computed for bacterial pathogen (including Hi, NTHi and Mcat) together and per pathogen. The incidence rate of AECOPD overall and associated to bacterial pathogen will be computed as well. The analysis will be done based on as clean as possible data. No study report will be written at this stage.
- A final analysis of all objectives will be performed when data obtained up to planned last patient last visit are available. A final study report will be written at this stage.

Description	Analysis ID	Disclosure Purpose (CTRS=public posting, SR=study report, internal)	Dry run review needed (Y/N)	Study Headline Summary (SHS)requiring expedited communication to upper management (Yes/No)	Reference for TFL
Final analysis	E1_01	Study report	YES	NO	See TFL TOC
Interim analysis	E1_02	Internal	NO	NO	See TFL TOC

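### The ± 14-day visit window in SAP 6.2 does not match the protocol's Table 6 interval and has no defined anchor date

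*SAP*

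**What the plan says.** **SAP 6.2 (Amendment 2, the current version).** On visit timing it says: "According to protocol, the interval of ± 14 days for any scheduled visit will not be a criterion for exclusion from the analyses". The next sentence plans an output from that window: "The number and percentage of patients with a stable visit within and without this time window will be presented". The footnote on stable visits displaced by an exacerbation uses the same width and gives the only anchor in the section: the visit is to be moved "within the ± 14 days' time window from the scheduled appointment, when the patient is stable again".

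**Protocol 6.3, Table 6.** For Visit 1 to Visit 2, and again for Visit 2 to Visit 3, the optimal interval is 182 days and the allowed interval is 175 to 203 days, counted from the preceding visit. A displaced visit follows the table: "the stable study visit should be rescheduled to a later date, when the subject is stable again and within the time window specified". There is an exception for the concluding visit, which after consultation with the sponsor "may however exceptionally be conducted outside of the allowed interval if necessary by the investigator". For Screening to Visit 1 the optimal length is ± 14 days and the allowed interval is "≤42 days before Visit 1". That screening row is the only place in Table 6 where ± 14 days appears.

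**The concern.** The planned table is where the SAP would show how far the stable visits kept to their timing. A reader would take it as compliance with the protocol. The SAP uses a symmetric window around a date it does not define. The protocol uses an asymmetric window counted from the previous visit. If the two windows differ, some visits that the protocol allows would be counted as out of window, and some that it does not allow would be counted as in. With no stated anchor, two programmers following the SAP could also produce two different tables.

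**Working it through.** **Inputs.** From protocol Table 6: optimal 182 days, allowed 175–203 days, Screening to Visit 1 allowed up to 42 days. From SAP 6.2: half-width 14 days, centre not stated.

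**1. The protocol window around its optimum.** 175 − 182 = −7 and 203 − 182 = +21. Length: 203 − 175 + 1 = 29 days. Midpoint: (175 + 203)/2 = 189.

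**2. The SAP window if centred on 182.** 182 − 14 = 168 and 182 + 14 = 196, also 29 days long. It has the same length as the protocol window but lies 7 days earlier.

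**3. Where the two disagree.**

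| Days from previous visit | SAP, centred on 182 | Table 6 |
|---|---|---|
| 168–174 (7 days) | in | out |
| 175–196 (22 days) | in | in |
| 197–203 (7 days) | out | in |

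**4. Other centres.** 183 ± 14 gives 169–197, with 6 discordant days at each end. 184 ± 14 gives 170–198, with 5 at each end. Only 189 ± 14 gives 175–203, and neither document names day 189 as a scheduled date.

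**5. Visit 3, if the appointment is counted from Visit 1.** 2 × 182 = 364, and 364 ± 14 gives 350–378. Chaining Table 6 gives 2 × 175 = 350 to 2 × 203 = 406. A Visit 3 on days 379–406 can therefore comply with Table 6 and still be flagged. Conversely, with Visit 2 on day 203 and Visit 3 on day 350, the Visit 2 to Visit 3 interval is 350 − 203 = 147 days. Table 6 does not allow that, yet day 350 lies inside 350–378.

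**6. Visit 1.** The SAP sentence covers every scheduled visit. If ± 14 days were applied from screening, a Visit 1 on days 15–42 would be flagged although Table 6 allows it.

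**7. Possible size, by assumption only.** Suppose intervals are normal with mean m and SD s. The share classified differently is P(167.5 < X < 174.5) + P(196.5 < X < 203.5). At m = 182 and s = 10 this is 0.153 + 0.058 = 0.211, and the in-window share is 85.3% under the SAP window centred on 182 against 75.8% under Table 6. For m of 180, 182, 185 or 189 and s of 5, 7, 10 or 14, the share runs from 2.8% (m = 185, s = 5) to 23.4% (s = 14, at m = 180, 182 or 189). These means and SDs are assumptions, not trial figures.

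**8. Version check.** SAP Amendment 2 cites Protocol Amendment 2. The protocol's amendment log shows 175–203 days in Table 6 at Amendment 1 and lists no change to it at Amendments 2 or 3, so a version gap does not explain the difference. SAP section 9 declares no change from planned analyses.

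**9. Reach.** SAP 6.2 says the window excludes nobody. In SAP 5.4.4, the only condition listed under the out-of-window code (2090) is sputum collected more than 96 hours after exacerbation onset. No estimate uses the ± 14 days.

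**The case against.** Four points can be made for the plan.

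- **The SAP never says 182.** Days 168–196 are an inference, and a centre of 189 would remove the conflict. This stands, so the misclassified days are stated conditionally. It also shows the second half of the problem: the window cannot be programmed until its centre is defined.
- **The appeal to the protocol may concern the non-exclusion rule, not the width.** The sentence can be read that way. The log for Protocol Amendment 2 shows a deleted sentence to that effect for the former per-protocol cohort. The width may come from the screening row of Table 6. It is therefore not established that the SAP credits a ± 14-day window to the protocol. On either reading the width still differs from Table 6 for Visits 2 and 3, and current protocol section 9.3 no longer contains the non-exclusion rule.
- **The footnote repeats a site-conduct rule that the protocol governs.** This is true, and sites would follow the protocol. It still leaves the SAP with a rule that Table 6 does not contain.
- **The output is descriptive.** SAP section 7 says: "All analyses are descriptive". This stands and limits the consequence.

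Three stronger readings are tempting, and the documents do not support them. A reader might infer that the counts are certain to be wrong; they differ only if visits fall on discordant days. A reader might take 14 discordant days out of 36 (168–203) as a 39% error rate; that needs visits spread evenly over exactly that range, which nothing supports. A reader might also infer that the wrongly flagged visits are mainly those of exacerbating patients. Rescheduling to a later date could push visits towards days 197–203, but half of the discordant days are early ones, and in the example in step 7 the early group is the larger (15.3% against 5.8%).

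**Conclusion.** The inconsistency between the documents is real and minor. The SAP's ± 14 days does not match the 175–203 days of Table 6 and has no defined anchor. If centred on the 182-day optimum, it reverses the status of 7 days at each end of the interval. The number of visits on those days cannot be derived from the documents, and the 3% to 23% range above rests wholly on assumed distributions. The effect is confined to the descriptive in-window and out-of-window table. A reader might infer that the primary results are at risk, but they are not: the window is not an exclusion criterion, so the primary proportions and their confidence intervals are the same under either definition.

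**What to change.** Reconcile the SAP and the protocol to one visit window before the table is programmed.

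- **Compliance sentence.** Define the table by the Table 6 interval and anchor for each visit: up to 42 days for Screening to Visit 1, and 175–203 days from the previous visit for Visits 2 and 3. Identify separately any Visit 3 held under the protocol's exception.
- **Rescheduling footnote.** Align it with the same window, or refer to Table 6 without restating a width.
- **Non-exclusion rule.** State it as an SAP decision and drop the appeal to the protocol, since current protocol section 9.3 does not contain it.

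The cost is an edit to two places in SAP 6.2 and the matching table specification. No data collection, sample size or primary analysis changes.

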6.2.1. Statistical methods: analysis of correlated Data Using Generalized Estimating Equations

Average proportion of sputum samples positive for bacteria/viruses and its 95% CI will be computed using a GEE model. GEE approach uses weighted combinations of observations to extract the appropriate amount of information from correlated data such as the response measurements across multiple stable visits on the same patient (Burton, 1998).

For the purpose of the analyses a binomial distribution for the response variable (presence or absence of bacterial/viral pathogens in the sputum) with logit as link function will be assumed and an exchangeable correlation matrix will be chosen to account for the within-patient correlations.

The exchangeable correlation matrix assumes that the correlation between any two responses of the i^{th} individual is the same.

CONFIDENTIAL

201112 (EPI-NTHI-001 BOD APA)
 Statistical Analysis Plan Amendment 2 Final

Other commonly used within-patient correlation matrices are as follows:

- Independence, repeated observations are uncorrelated
- Unspecified (unstructured), correlations within any two responses are unknown and need to be estimated
- Autoregressive of first order [AR(1)], assuming the interval length is the same between any two observations. Measurements taken further apart are less correlated than those taken closer together.

The model with the exchangeable correlation matrix will be adopted in the main analysis. Models with the other matrices could be run as sensitivity analyses. QIC and the related QICu statistic will be used to compare GEE models with different correlation matrices.

SAS codes

```
ods output ParameterEstimates=out_parm ClassLevels=Class;
proc genmod data=<dataset> descending;
  class pid;
  model y = / dist = bin link = logit lrci ;
  Repeated subject=pid/sorted corr=cs PRINTMLE;
  by bacteria visit;
run;

data result;
  set out_parm(where=(parameter='Intercept') drop=ChiSq ProbChiSq DF);
  format percent LL UL percent8.1;
  Percent=exp(estimate) / (1+exp(estimate));
  LL=exp(LowerLRCL) / (1+exp(LowerLRCL));
  UL=exp(UpperLRCL) / (1+exp(UpperLRCL));
  unit=_N_;
run;
```

where pid = personal identifier, y = positivity to pathogen (0, 1), bacteria = type of bacteria, visit = type of visit (stable or exacerbation).

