6.3.3.2. Sputum sample quality

Sputum sample quality will be summarized (squamous cell count, neutrophils cells count and bacteria direct smear) at any stable visit and at any mild, moderate or severe AECOPD visit. Sputum sample characteristics will be also summarized by bacterial and /or viral presence in any stable visit and in any exacerbation visit.

Sputum quality, derived as detailed in section [11.2.3](#), will be tabulated given the type of visit.

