11.2.3. Sputum Quality

The quality of sputum is defined as follow:

- < 10 squamous epithelial cells/field: sample of good quality
- 10-25 squamous epithelial cells/field with significant numbers of cells derived from the lower respiratory tractus (ciliary epithelial cells, bronchial cells, round cells): sample of moderate quality
- > 25 squamous epithelial cells/field: sample of bad quality

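### The 10% trigger for the sputum-quality re-analysis is set on one overall rate while the primary proportions are estimated by state, and the quality classes behind it leave a gap

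*SAP*

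**What the plan says.** SAP 6.2 sets the rule: "If more than 10% of sputum samples have bad quality (as defined in section 11.2.3), the analyses for primary objective will be repeated". Only part of the data enters that second run, which is done "in the subset of sputum samples of good and moderate quality". The rule does not name a visit type or a denominator.

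The estimates this check supports are split by state. SAP 6.2 computes the proportions at stable visits and at exacerbation visits, and the model code in SAP 6.2.1 runs by pathogen and by visit, where "visit = type of visit (stable or exacerbation" are the two levels.

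SAP 11.2.3 defines three classes:

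- good: "< 10 squamous epithelial cells/field: sample of good quality"
- moderate: "10-25 squamous epithelial cells/field with significant numbers of cells derived from the lower respiratory tractus"
- bad: "> 25 squamous epithelial cells/field: sample of bad quality"

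SAP 6.3.3.2 summarises quality descriptively, "at any stable visit and at any mild, moderate or severe AECOPD visit", and tabulates the derived quality class by type of visit. It does not link those tables to the re-analysis. No elimination code in SAP 5.4.4 removes bad-quality samples. Code 2120 covers a smear not prepared or not assessed, and its effect is judged case by case.

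**The concern.** There are two separate defects in one rule.

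First, the trigger works at a different level from the estimates. Each patient has three scheduled stable visits, against one AECOPD visit on average in the sample-size assumptions, so the pooled rate is mostly a stable-visit rate. A quality problem confined to one state is diluted by the other. Collection conditions do differ: the protocol allows home self-collection in specific AECOPD cases (6.4.3.9) and bars it at scheduled visits (6.4.2.15). Unequal quality is therefore possible, in either direction.

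Second, the trigger counts bad samples while the re-analysis keeps good and moderate ones. These would be complements only if every sample had a class, and the middle squamous-cell band is classified only when lower-tract cells are also present.

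At stake is whether the only pre-specified quality-restricted analysis of the primary objective is produced for the state that needs it.

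**Working it through.** **Inputs from the documents.** Enrolment 200, participation 90%, one AECOPD visit on average, 80% giving an evaluable sample (Protocol 9.2); three stable visits in the primary analysis (SAP 6.2); threshold 10% (SAP 6.2).

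**Assumed, because the documents give no figure.** The number of stable samples S and the bad-quality rates x (AECOPD) and y (stable).

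**The plan's own figure.** 200 × 0.90 × 1 × 0.80 = 144 AECOPD samples, against around 140 stated.

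**Pooled rate.** (A·x + S·y)/(A + S), with A the number of AECOPD samples.

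Take A = 144 and S = 200 × 0.9 × 3 × 0.9 = 486, total 630 (the last 0.9, the share sampled, is assumed):

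- x = 20%, y = 6%: (28.8 + 29.2)/630 = 9.2%. Silent.
- x = 2%, y = 12%: (2.9 + 58.3)/630 = 9.7%. Silent.
- x = 20%, y = 8%: (28.8 + 38.9)/630 = 10.7%. Fires.
- x = y: the pooled rate equals the common rate, so pooling has no effect.

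With x = 20%, the rule is silent while y is at most (63 − 28.8)/486 = 7.0%.

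**Range over S, with A = 140.** The largest AECOPD bad share that leaves the rule silent is (floor(0.10·(A + S)) − round(y·S))/A. The largest stable share, if no AECOPD sample is bad, is 0.10·(A + S)/S. The last column is the chance that the pooled rule fires at true rates of 20% (AECOPD) and 5% (stable), treating samples as independent.

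| S | Largest silent AECOPD share, y = 5% | Largest silent stable share, x = 0 | P(fires), 20% / 5% |
|---|---|---|---|
| 300 (3 × 200 × 0.5) | 29/140 = 20.7% | 14.7% | 0.395 |
| 432 (3 × 200 × 0.9 × 0.8) | 35/140 = 25.0% | 13.2% | 0.115 |
| 540 (3 × 200 × 0.9) | 41/140 = 29.3% | 12.6% | 0.029 |
| 600 (3 × 200) | 44/140 = 31.4% | 12.3% | 0.012 |

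A rule applied to AECOPD samples alone fires from 15 of 140 (10.7%), with probability 0.999 at a true rate of 20%. Dilution works both ways, but there is more room in the smaller group: stable shares can exceed 10% only modestly before the pooled rule fires.

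**Sensitivity to the number of AECOPD samples.** With two AECOPD visits per subject, A = 288. The 20% / 6% case then pools to (57.6 + 29.2)/774 = 11.2% and fires; the rule is silent only while y is at most (77.4 − 57.6)/486 = 4.1%.

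**Class gap.** This needs no assumption about rates: 10-25 squamous cells without significant lower-tract cells meets none of the three definitions. To illustrate the size, if 8% are bad and 5% unclassified, 13% of samples fall outside good and moderate. The trigger sees 8%, or 8/95 = 8.4% if unclassified samples leave the denominator, and does not fire.

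**The case against.** The strongest reply is that little depends on the trigger. It adds a supportive repeat and does not alter the main estimate. SAP 7 describes all analyses as descriptive. SAP 6.3.3.2 already reports quality by visit type, and sample characteristics by pathogen presence within each state, so an imbalance would be visible. All of this stands. What remains is that seeing an imbalance obliges nobody to run the re-analysis.

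The second reply is that the examples are chosen. That is also fair: no bad-quality rate appears in the documents, both silent examples lie just under 10%, and modest changes make the rule fire. The table shows that silence is not confined to those two cases, but not how likely it is in this study.

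Third, pooling is inferred from unqualified wording, and the study procedures manual or central laboratory manual, to which Protocol Table 8 refers for quality components, may settle the middle band. If so, the SAP should say it. If the re-analysis does run, unclassified samples drop out on a literal reading, which is conservative.

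Two stronger readings are tempting. A reader might infer that AECOPD samples are the poor ones and will slip through. Nothing in the documents says so; if stable samples are worse, 15% stable and 5% AECOPD gives (72.9 + 7.2)/630 = 12.7% and the rule fires. A reader might also infer that the rule biases the reported primary proportion. It does not: that proportion is the same whether or not the trigger fires, and the documents give no positivity for bad against adequate samples from which to compute a bias.

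**Conclusion.** The point holds as a mismatch between the trigger and the estimates it supports, and as a gap in the class definitions. On the natural pooled reading, with about 140 AECOPD and 300 to 600 stable samples and 5% of stable samples bad, the re-analysis is not required until the AECOPD bad share passes roughly 21% to 31%. In the other direction, the stable share can reach about 12% to 15% if no AECOPD sample is bad. These limits rest on assumed stable counts and bad-quality rates and on one AECOPD sample opportunity per patient; they shrink with more AECOPD samples and disappear when the two rates are equal. The consequence is a missing supportive analysis for one of the two primary estimates, not a changed primary result. The class gap follows from the text alone, but how many samples it affects is unknown.

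**What to change.** In SAP 6.2, either apply the 10% threshold separately to samples from confirmed stable visits and from AECOPD visits, repeating the analysis for any state that exceeds it, or run the good-and-moderate analysis for both states unconditionally. The unconditional version is simpler and removes a data-dependent decision.

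If a trigger is kept, define it as the share of samples not classed as good or moderate, so that trigger and subset are complements. State the denominator, including how samples with no quality reading are treated.

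In SAP 11.2.3, have the laboratory assign samples with 10-25 squamous cells and no significant lower-tract cells to a stated class. Which class is a laboratory judgement.

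The cost is a few SAP sentences and possibly one extra set of supportive tables. No new data are needed.
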